This IRB application also covers a secondary study, to additionally study biological correlates of antenatal anxiety (i.e., immune and endocrine functioning) in a subset of women from the main trial: 200 drawn from our randomized trial (100 intervention, 100 usual care), as well as 100 healthy women without anxiety or depression. The aims of the secondary study are as follows:

**Aim 1:** To characterize the “immune phenotype” of anxious women across the peripartum, specifically by measuring the relation among anxiety symptoms and peripheral markers of inflammation (IL-6, CCL3, CXCL8, Eotaxin, VEGF, and GM-CSF, as supported by our preliminary data) within and across women (both anxious and healthy) and between those receiving the intervention and control.

**Aim 2:** To determine the relation between levels of allopregnanolone (ALLO) in pregnancy and 1) concurrent anxiety symptoms and 2) future symptoms of postpartum depression (PPD).

**Aim 3:** To examine the relation between changes in immune functioning (Aim 1) and ALLO levels (Aim 2) in anxious pregnancy across time.

**Aim 4:** To examine whether immune function and/or ALLO are mediators or moderators of the association between antenatal anxiety and poor birth outcomes (specifically, preterm birth and small-for-gestational age).

To supplement our study, we will collect qualitative data as part of a process evaluation to better understand women's experiences with the intervention (e.g. how it can be improved). Given the recent effects of COVID-19 on our participants and our study, we will also inquire about how the telephone format of our intervention is being received by our participants, as well as try to learn about the impact of social-distancing and other aspects of the COVID-19 situation on pregnant women generally.

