For the secondary biological study, a sample size of 60 subjects in each group, women with anxiety (with and without intervention) and healthy controls, will give us at least 80% power to detect a difference in means of log-transformed cytokines across groups with an effect size of 0.3 to 0.5. This calculation assumes four repeated measurements with exchangeable covariance structure, a correlation of 0.6 and alpha level = 0.05. The smallest observed effect size for CCL3 between anxious and non-anxious women in the preliminary data of 51 women was 0.3 in 1nd trimester to 0.5 in the 2nd trimester (Cohen's D from 0.3 to 0.5). Sample size calculations were performed using the PASS Sample Size Software program.(34) Prior studies in our clinic have an attrition rate of up to 20%, but because the attrition rate for this type of study in Pakistan is unknown we will increase our sample size to account for higher attrition (up to 40%). We will therefore enroll 300 women to yield an ultimate sample size of at least 180.

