Pregnancy conditions: medical status in pregnancy (e.g. pre-eclampsia, gestational diabetes)	X			X	X	X
Adverse event review					AT ALL TIMES	

\*Baseline assessment may be the same day or up to two weeks after screening.

Note: Full descriptions of the assessment tools are given in section 8.2.3.

\*\*Assessments will be somewhat flexible; the 6-week postpartum visit can be done a week early and up to three weeks after the 6 week mark (if scheduling issues preclude collecting data exactly at the desired time)

§This screener will be administered in order to be able to refer women with IPV to counseling, since it is considered an adverse event.

§§Anthropometry will be measured either our team or a healthcare provider at the 6 week postpartum visit.

[figure not shown]
2. Describe the number and type of study visits and/or contacts between the study team and the participant, how long they will last, and where/how they will take place.

For the assessments there will be a screening visit at the time of enrollment, visit at baseline (either at the same time if the woman is ready to enrol or within 2 weeks afterwards if she would like more time to think about it), in late pregnancy, at delivery, and at 6 weeks postpartum. See above for assessments that will be done at each visit. We expect baseline and the 6 week postpartum visits to last between 1 to 1.5 hours. We expect the 3rd trimester visit to be shorter, around 45 minutes. We expect the birth visit to only entail 5 minutes of data collection with the women, while the rest will be gathered from medical records.

For women randomized to the intervention, there will be 6 core intervention sessions and up to 2-6 booster sessions (depending on the time of enrolment). The first five core sessions will be delivered weekly as early in the pregnancy as possible, then the booster sessions will occur, with one final core session (Core Session 6) in the 3rd trimester. Booster sessions will be scheduled on a case by case basis, depending on the recruitment time of the pregnant mother. Please see Table 2 above for an outline of session content.

For women in the biological substudy, there will be an additional visit at 24 weeks gestation for a blood draw and HADS administration. See the Figure below for a timeline of study visits.

Figure: Timeline for participants in the intervention and control arms of the main trial

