#### Analysis of Variables from Biological Substudy

**Statistical Analysis.** Oversight for the statistical analyses will be provided by [name] of the Johns Hopkins Biostatistics Center. The initial statistical approach will include a descriptive cross-sectional analysis at each time point, both for quality assurance and to attain a better understanding of the distributions of the outcome variables for use in subsequent analyses, including the need for any transformations, followed by the longitudinal analyses. For **Aim 1**, we will assess the associations between cytokine levels as dependent variables and level of anxiety (as measured by the HADS) as the independent variable. The level of anxiety will be considered from the following perspectives: 1) dichotomous (above and below HADS=8) and 2) continuous. In both analyses, we will compare women with anxiety vs. healthy controls and with and without the intervention to evaluate whether there is a positive association between

cytokines and other immune markers with anxiety. In addition, we will perform a comparison of immune markers between women disease/intervention groups adjusted for potential confounders that are differentially distributed by disease group, using multivariable linear regression model at each time point. We will assess whether association between immune marker and anxiety is different by group and by visit. In the longitudinal analyses, we will fit generalized linear mixed effect models to account for within-woman correlation of inflammatory markers. The model will include indicators for visit and group as well as any relevant interaction terms (e.g. group by visit). The models will adjust for baseline severity and other patient characteristics. A random effect for woman will be included as a random intercept. Other, more complex model structures will be explored, such as a model with random slope or non-independent residual correlation structure. These models account for missing at random, i.e. missing data are assumed to depend on prior immune marker values and covariates. Standard model checking will be performed and the most parsimonious model will be selected based on the Akaike Information Criterion (AIC).

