## Missing Data

Adjusted analysis and subgroup analysis will be based on covariates at baseline without non-missing values. Sensitivity analysis will be performed on the covariates with missing values imputed (133). Detailed imputation methods will be described in the statistical analysis plan. All analyses will be detailed in the statistical analysis plan, which will be finalized before un-blinding the study.

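### If baseline severity means HADS anxiety, adjusting the Aim 1 longitudinal model for it can shrink the anxious-versus-healthy level contrast or cost it much of its power

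*Combined protocol and SAP*

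**What the plan says.** Aim 1 of the secondary study (section I) relates anxiety symptoms to immune markers "within and across women (both anxious and healthy) and between those receiving the intervention and control". There are three groups: HMHB, enhanced usual care (EUC) and healthy controls. The two randomised arms require HADS anxiety of 8 or more. Every description of the healthy group (sections III.A, IV and Study Implementation) requires HADS anxiety below 8.

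Section III.B sizes the substudy at 60 analysed women per group, for "at least 80% power to detect a difference in means of log-transformed cytokines across groups with an effect size of 0.3 to 0.5". It assumes four exchangeable measurements with correlation 0.6 and alpha 0.05, and takes the effect size from anxious and non-anxious women in preliminary data.

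The section Analysis of Variables from Biological Substudy first plans analyses with HADS as the exposure, split at 8 and continuous: "In both analyses, we will compare women with anxiety vs. healthy controls and with and without the intervention". It then plans regressions by group at each visit, adjusted for confounders. For the longitudinal mixed model it says "The model will include indicators for visit and group as well as any relevant interaction terms", and next "The models will adjust for baseline severity and other patient characteristics". This is the only mention of baseline severity. Neither a scale nor a visit is given, and nothing limits the covariate to HMHB versus EUC.

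**The concern.** Adjusting a randomised comparison for baseline severity is ordinary and usually helpful. The healthy group, however, is not randomised: it is defined by a low anxiety score. If severity is HADS anxiety at screening, anxious and healthy women do not overlap on the covariate at all. The group coefficient then compares women on either side of the cut by extrapolating to a common HADS value. It no longer estimates the difference in group means.

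At stake is how that coefficient is read. If markers rise with anxiety, part of the anxious-versus-healthy difference moves into the severity term, and the group term could be reported as no difference. The other Aim 1 analyses might show the association, and the plan has no rule for reconciling the two.

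**Working it through.** **Inputs.** From section III.B: 60 per group, four visits, exchangeable correlation 0.6, alpha 0.05, d = 0.3 to 0.5. Sidedness is not stated; two-sided is assumed. The documents give no HADS distribution and no shape for the marker-HADS relation, so both were varied.

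**The plan's own figures.** Enrolment: 180/(1 - 0.40) = 300, as stated. Variance of a woman's four-visit mean: (1 + 3 × 0.6)/4 = 0.70. Standard error for 60 versus 60: sqrt(0.70 × 2/60) = 0.153. Power at d = 0.5: Φ(0.5/0.153 - 1.96) = 90.5%. At d = 0.3 it is 50%, so the stated 80% is met at the upper end of the range and not at the lower. That is a separate matter, and nothing below depends on it.

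**Why a HADS covariate matters.** Suppose the marker mean is a + b × HADS. The groups then differ by d = b × (difference in mean HADS). With HADS and group both in the model, the HADS term takes all of d and the group coefficient is zero. Suppose instead that the marker steps at 8. The group coefficient is then unbiased, but group and HADS are collinear: the variance inflation factor is about 4, so the standard error about doubles.

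**Simulation.** Three groups of 60; integer HADS, 8-21 in anxious and 0-7 in healthy women. Four distributions: N(8,4) cut at 8, and anxious/healthy N(11,3)/N(4,2), N(10,2)/N(4,2) and N(12,3)/N(3,2), with the second number the SD. Woman-level means were regressed on group and HADS, with 2000 datasets per cell. For a separate baseline HADS, a retest SD of 2-3 points was assumed. The last row is a formula, not a simulation.

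EUC versus healthy, coefficient and rejection rate:

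| Covariate | Marker shape | d = 0.5 | d = 0.3 |
|---|---|---|---|
| None | any | 0.50; 90.5% | 0.30; 50% |
| Screening HADS | linear | about 0; 4-5% | about 0; 4-5% |
| Screening HADS | half linear, half step | 0.24-0.26; 13-19% | 0.14-0.16; 8-9% |
| Screening HADS | step at 8 | unbiased; 43-60% | unbiased; 19-26% |
| Separate baseline HADS | linear | 0.20-0.38; 12-49% | 0.12-0.23; 7-21% |
| Separate baseline HADS | half linear, half step | 0.35-0.43; 29-59% | 0.21-0.26; 14-27% |
| Separate baseline HADS | step at 8 | unbiased; 54-77% | unbiased; 24-36% |
| Baseline marker level | stable difference | 0.20; 43% | 0.12; 19% |

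**Baseline marker row.** The difference left at the three later visits is (1 - 0.6)d. Residual variance: (1 + 2 × 0.6)/3 - 0.6² = 0.373. Standard error: sqrt(0.373 × 2/60) = 0.112. At d = 0.5: Φ(0.20/0.112 - 1.96) = 43%.

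**Pooled contrast.** A separate simulation of 120 anxious versus 60 healthy women agrees. By formula, unadjusted power is 97% at d = 0.5 and 62% at d = 0.3. With HADS added, the step case falls to 51% and 20%, and the linear case to 4-5% with a coefficient near zero.

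**What is not affected.** HMHB versus EUC with severity in the model: mean within 0.01 of the true zero, empirical SD 0.15-0.16. In a four-visit group-by-visit model with a time-fixed HADS term, changes from visit 1 were identical with and without it (SE 0.163 both ways), while the level SE rose from 0.153 to 0.233. With 39% monotone dropout the changes moved by less than 0.001.

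**The case against.** A reader might infer that the planned adjustment removes the anxious-versus-healthy difference, or that Aim 1 fails. The documents do not support either.

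- **Severity is not said to be HADS anxiety.** The same section calls HADS the level of anxiety and uses a different term for the covariate. This stands: the harm through HADS is conditional on that reading.
- **A coefficient near zero needs two further conditions.** The covariate must be the score that formed the groups, and the marker must be roughly linear in it. Table 4 lists a separate baseline HADS for substudy women, which is the more natural meaning of baseline and gives attenuation or power loss, not removal. One caution: "Baseline assessment may be the same day or up to two weeks after screening", so the two scores may be close.
- **The contrast is inferred.** Section III.B names no model and no pairwise contrast, and the longitudinal model may include a group-by-visit interaction. Linking the sizing to the group level term is reasonable, but it is not stated text.
- **Other analyses cover the association.** The HADS-exposure analyses and the per-visit regressions do not name severity and are not counted as affected. This lowers the weight.
- **The SAP can settle it.** "All analyses will be detailed in the statistical analysis plan, which will be finalized before un-blinding the study". Deferral leaves the definition open, but the adjustment itself is already stated, so an SAP that follows the plan would carry it forward.
- **Model selection might drop the term.** The plan says "the most parsimonious model will be selected based on the Akaike Information Criterion" but not that this selects covariates. If it does, the step case at d = 0.5 mostly recovers (severity kept in 15-18% of datasets, power 84-86%). The linear case does not (kept in 74-94%, contrast significant in 9-26%).

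**Conclusion.** The point holds in conditional form. The plan states an unrestricted adjustment for an undefined baseline severity in a model whose groups include healthy controls. Each reading computed either biases the anxious-versus-healthy level contrast or cuts its power. At d = 0.5 and 60 per group, power of about 90% falls to 43-60% with the screening HADS and a pure step at 8. Attenuation to about zero requires the screening score and a near-linear marker. A separate baseline HADS costs less, and the baseline marker level leaves 40% of a stable difference.

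These sizes rest on assumed HADS distributions, marker shapes and retest SD; the near-zero linear result held under every distribution tried for the screening score. The documents do not show harm to HMHB versus EUC, to between-visit changes in complete data, or to the HADS-association and per-visit analyses. Priority is minor: one contrast of one substudy model.

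**What to change.** In the SAP:

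1. Define baseline severity by scale and visit.
2. Use it only for the HMHB versus EUC contrast, or in models within anxious women.
3. Adjust the healthy-control level contrasts for confounders only, and state that HADS anxiety and the baseline marker level are not among them.
4. Keep models with both HADS and group for the planned test of whether the marker-anxiety association differs by group, but do not report their group main effect as the anxious-versus-healthy difference.

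The cost is one definition and a few sentences of SAP wording. No extra data or visits are needed.

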Our main innovation is a focus on reducing anxiety; while anxiety and depression often co-occur,(74) prenatal anxiety, especially early in pregnancy, has been neglected. Exposure to anxiety, even as early as during the second trimester of pregnancy, is important to intrauterine fetal growth.(43, 44) Given the high prevalence of adverse birth outcomes in

Pakistan,(e.g., 47% of newborns in Pakistan are SGA),(46) this setting provides a unique research opportunity. Contrasting with current initiatives (that do not address anxiety), our proposed intervention specifically targets symptoms of anxiety, using strategies based on CBT. This approach is known to effectively treat CMDs,(37, 38, 75) but it has been underused for prevention in both high- and low-income countries despite evidence-based recommendations.(76) As both clinical and subthreshold prenatal anxiety strongly predicts depression,(15) we expect our anxiety-focused intervention to have carry-over benefits on depression as well as anxiety. By creating and testing an intervention in the early- to mid- pregnancy, we will provide critically needed evidence of the effectiveness of these approaches in reducing prevalence of both of these damaging maternal conditions and their collateral effects on newborns. By targeting pregnant women with subthreshold anxiety while simultaneously including women with high anxiety levels, we aim to both prevent and treat GAD and prevent CMDs (i.e., postpartum GAD and MDE). We will do this using non-specialist providers and integrating the program into tertiary care.

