For **Aim 2**, we will follow the same approach, with ALLO levels as the independent variables and anxiety as the dependent variable. Generalized linear mixed effects models will be fit to the data to model anxiety trajectories while accounting for within-women correlation of these measures. Estimated anxiety trajectories and ALLO levels will be used as candidate independent variables in a logistic regression model of risk of PPD. Cross-validated area under the curve will be used to assess model discrimination between women with and without PPD.

For **Aim 3**, we will assess the associations between ALLO levels and immune markers at different times during pregnancy by disease/intervention group and will fit similar generalized linear mixed effects models described in Aims 1 and 2. These models will first be fit for each immune marker separately and then combined into a multilevel model with crossed random effects that includes with random intercepts for woman and immune marker to “borrow information” across multiple immune markers within the woman.

For **Aim 4**, our analysis will focus on the association of perinatal anxiety and birth outcomes, specifically assessing mediation in both cross-sectional and longitudinal analyses partitioning the total effect of anxiety on birth outcomes as direct and indirect, through change in cytokine and hormone levels.

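### Aim 2 asks how ALLO in pregnancy relates to later postpartum depression, but the only measure named is the AUC of a model that also contains anxiety, and no ALLO-specific estimate is planned

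*Combined protocol and SAP*

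**What the plan says.** In Aims of the Study, Aim 2 of the secondary study reads: "To determine the relation between levels of allopregnanolone (ALLO) in pregnancy and 1) concurrent anxiety symptoms and 2) future symptoms of postpartum depression (PPD"). It therefore sets two questions about ALLO, one on anxiety and one on PPD.

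Under Analysis of Variables from Biological Substudy, the anxiety question gets a mixed model: "we will follow the same approach, with ALLO levels as the independent variables and anxiety as the dependent variable". The PPD question gets one logistic regression: "Estimated anxiety trajectories and ALLO levels will be used as candidate independent variables in a logistic regression model of risk of PPD". The single measure attached to it is: "Cross-validated area under the curve will be used to assess model discrimination between women with and without PPD".

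No section names a PPD model containing ALLO without anxiety, an ALLO–PPD odds ratio, interval or test, or a comparison of models with and without ALLO. The mediation work under Aim 4 concerns birth outcomes, not PPD. The Missing Data section promises a full statistical analysis plan, but the document supplied contains only this brief one.

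**The concern.** The aim is about one predictor, while the reported measure describes two predictors together. Background and Rationale states: "As both clinical and subthreshold prenatal anxiety strongly predicts depression,(15) we expect our anxiety-focused intervention to have carry-over benefits on depression". On that premise the joint AUC should exceed 0.5 whether or not ALLO matters, so a good AUC says nothing about ALLO by itself.

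Turning to the ALLO coefficient in the joint model helps only in part. That coefficient describes ALLO among women with the same anxiety trajectory. Background and Rationale links low ALLO to anxiety outside pregnancy, so some or all of an ALLO–PPD relation may be shared with anxiety, and adjustment removes the shared part. If the estimated trajectories come from the mixed model that already has ALLO as a predictor, the overlap is greater still.

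At stake is whether the substudy, with blood drawn from up to 300 women, reports a number that answers the second half of Aim 2.

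**Working it through.** **Inputs from the documents.** Enrolment is 100 intervention, 100 enhanced usual care and 100 healthy controls, with up to 40% attrition. The trial arms require HADS anxiety of 8 or more, and healthy controls score below 8. Background gives 35% to 49% of pregnant women in Pakistan as anxious.

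**Inputs assumed, because no figure is given.** Odds ratio (OR) of PPD per SD of anxiety: 1.5 to 3. ALLO–anxiety correlation: -0.3 or -0.5. PPD rate: 15–25%, or 10–30% in steps 2 and 3. The nearest stated rate is the main trial's 30% for common mental disorders. Tests are two-sided at 5%.

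**Step 1: the plan's own figure.** 180 / (1 - 0.40) = 300, which matches "We will therefore enroll 300 women to yield an ultimate sample size of at least 180". Per group, 100 × 0.60 = 60, so the final sample is 120 anxious and 60 healthy women. The stated power assumptions, "four repeated measurements with exchangeable covariance structure, a correlation of 0.6 and alpha level = 0.05", belong to the cytokine comparison. No power is stated for ALLO and PPD.

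**Step 2: joint AUC when ALLO is irrelevant.** Model: logit P(PPD) = a + ln(OR) × anxiety, with ALLO independent of both. n = 180, 1,000 simulated trials per setting, 10-fold cross-validated AUC, sample not selected on anxiety. Above chance means above 0.5 + 1.96 null standard errors. That threshold is assumed; the plan has none.

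| Anxiety OR per SD | Mean joint AUC | Above chance |
|---|---|---|
| 1.5 | 0.54–0.58 | 16–44% |
| 2.0 | 0.62–0.65 | 44–86% |
| 2.5 | 0.68–0.69 | 72–98% |

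Anxiety alone gives an equal or slightly higher AUC (0.55–0.70). Adding ALLO changes the AUC by -0.005 to -0.011 on average, so the AUC change correctly shows that ALLO adds nothing. The ALLO coefficient is also well behaved here, rejecting in 3.8–5.7% of trials given anxiety and 3.5–5.5% alone.

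**Step 3: ALLO related to PPD only through anxiety.** ALLO = r × anxiety + √(1 - r²) × noise, with PPD depending on anxiety only (OR 2.5) and the sample again unselected. ALLO alone rejects in 16–29% at r = -0.3 (median ALLO OR 0.78–0.79) and 40–68% at r = -0.5 (0.65–0.66). Given anxiety, ALLO rejects in 4–9% (median OR 0.88–1.03), including settings where anxiety is measured with reliability 0.8.

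**Step 4: the same with the planned sampling.** 120 women above and 60 below an anxiety cut-off, with 42% of screened women above it, since (35 + 49) / 2 = 42. Anxiety OR 1.5 to 3, PPD 15–25%.

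| PPD model | Power, r = -0.3 | Power, r = -0.5 |
|---|---|---|
| ALLO alone | about 7–27% | about 13–63% |
| ALLO + intervention indicator | not tabulated | about 12–50% |
| ALLO + three-group indicator | not tabulated | about 7–18% |
| ALLO + anxiety | about 3–6% | about 3–6% |

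The three-group row is low because healthy controls are defined by HADS anxiety below 8. A three-group term is therefore dichotomised anxiety and removes most of the shared relation.

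**The case against.** Much of the case on the other side stands.

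- **No AUC rule.** A reader might infer that Aim 2 would be declared supported whenever the joint AUC exceeds 0.5. The plan says only that AUC will assess discrimination, and the percentages above chance in step 2 use a threshold supplied for this check. If the ALLO coefficient is read instead, the error rate with no ALLO relation stays near 5%.
- **Direction is not settled.** A reader might infer that anxiety is a hypothesised step from ALLO to PPD, so that adjusting for it is simply wrong. Having anxiety as the dependent variable in a regression does not establish that. Aim 4 considers ALLO as a possible mediator or moderator of the effect of anxiety, on birth outcomes, which as mediation puts anxiety first. On that ordering anxiety could confound the ALLO–PPD relation, and the unadjusted coefficient would not be the answer by itself.
- **Room for other fits.** The template asks for a brief plan, detail is deferred, and calling the predictors candidates permits an ALLO-only model. It does not specify one, and no selection rule is given for this model. The AIC rule stated for the immune-marker models, if carried over, would tend to drop ALLO when its relation is shared with anxiety.
- **Modest gain.** At anxiety OR 1.5 the ALLO-only model has little power too. This is one half of one aim of a secondary substudy.

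What remains is that the named measure cannot be attributed to ALLO and no ALLO-specific result is planned.

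**Conclusion.** The point holds as a minor improvement. The specified PPD analysis does not report the relation that Aim 2 asks about. The joint AUC mixes ALLO with a predictor that the protocol calls strong, and the joint ALLO coefficient covers only what is not shared with anxiety.

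The logic does not depend on the assumed inputs; the size does. In the scenario least favourable to the joint model (ALLO acting only through anxiety, planned sampling), power is about 7–27% or 13–63% for ALLO alone, at correlations of -0.3 and -0.5, against about 3–6% given anxiety. A direct ALLO effect would narrow the contrast in relative terms. The documents support neither a claim that the plan would produce false ALLO findings nor a claim that the unadjusted model alone is right. The primary endpoint and main trial are untouched.

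**What to change.** In the Aim 2 paragraph of Analysis of Variables from Biological Substudy, or in the promised statistical analysis plan:

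1. Report the ALLO–PPD odds ratio with 95% CI from a model without anxiety trajectories. Include at most an intervention indicator, not a three-group term.
2. Report the anxiety-adjusted ALLO odds ratio with 95% CI beside it, labelled as a separate question. Describe both as associations, since the documents do not settle whether anxiety precedes or follows ALLO.
3. For the joint model, report the change in cross-validated AUC and a likelihood-ratio test between models with and without ALLO, not the joint AUC alone.

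The cost is a few sentences and one or two extra model fits on data already planned, with no added women, visits or assays. The downside is that the incremental AUC will look less favourable than the joint AUC.

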#### Follow-up (6 weeks postpartum):

The primary endpoint will be assessed at six weeks postpartum (with flexibility for -1 week and +4 week window if needed because of scheduling reasons). Women returning for their routine 6-week postpartum visit will be asked to undergo a final follow-up assessment conducted by the Assessment Team, who will be masked to the allocation status of trial participants. Women in the biological substudy will also have a blood draw (using same techniques described above under 'baseline visit'). We will also administer the *Ages & Stages Questionnaire, Third Edition (ASQ-3)* to the infants of all participants in the trial to assess infant neurobehavioral functioning.

For the detailed description of the outcomes and time points, see **Table 4** below.

In the chart below, data collection procedures that are specific to the substudy are marked as Os in the chart instead of as Xs.

Table 4: Schedule of study assessment activities

	Screening	Baseline *	2 nd trimester	3 rd trimester**	Birth	6 weeks postpartum **
	Time 1	Time 2	Time 3	Time 4	Time 5	Time 6
Informed Consent	X	X				
Eligibility assessment						
Screening step 1 (age, residence, stage of pregnancy, language)	X					
Screening Step 2 (medical exclusions)	X					
Screening Step 3 (HADS anxiety inclusion)	X					
Screening Step 4 (SCID MDE exclusion)	X					
Assessments						
Socio-demographic questions		X				
PSS-10 (stress)				X		X
PES-Brief (pregnancy anxiety)		X		X		
PHQ-9 (depressive symptoms)						X
HADS (anxiety symptoms)	X	O	O			X
HADS (symptoms of depression)	X	O	O			X
MDE diagnosis (from SCID)	X					X
MSPSS (social support)	X		X			X
MRQ (relationships)	X		X			X
Empowerment	X					X
WHO-DAS (disability)	X		X			X
DHS IPV items (violence)						X
IPV Screening Question		X		X		(in the DHS module)
PAAS (behavioral activation)		X		X		X
Breastfeeding					X	X
Parenting self-efficacy						X
PBQ (bonding)						X
MIRI (maternal responsiveness)						X
MSEQ (maternal self-efficacy)						X
Anthropometry§§						X
Economic Data						
CSRI				X		X
Blood Draw (for biology aims)	O	O	O			O
Ages & Stages Questionnaire, Third Edition (ASQ-3)						O
From medical records						
Fetal outcome: SGA in utero*				X		
Pregnancy conditions:				X		
Birth outcomes: SGA, PTB, LBW					X	
Medications	X			X		X

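### Aim 2 asks how pregnancy ALLO relates to later depressive symptoms, but the only depression analysis planned is of a binary, undefined PPD outcome, and the scheduled six-week symptom scores are not used for it

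*Combined protocol and SAP*

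**What the plan says.** Section I (Aims of the Study) sets two targets for ALLO in pregnancy under Aim 2 of the secondary study: concurrent anxiety symptoms, and "future symptoms of postpartum depression (PPD".

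The section on analysis of the biological substudy handles the first target with mixed models for anxiety. For the second it says that the estimated anxiety trajectories and the ALLO levels "will be used as candidate independent variables in a logistic regression model of risk of PPD". Performance is judged as follows: "Cross-validated area under the curve will be used to assess model discrimination between women with and without PPD". No other depression analysis is given for Aim 2, and the text does not say how PPD is determined or how many candidate predictors there are.

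Table 4 lists three depression measures at six weeks postpartum: "PHQ-9 (depressive symptoms", the HADS depression subscale, and "MDE diagnosis (from SCID". The first two are scores and the third is a diagnosis.

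On size, Section III item B says: "We will therefore enroll 300 women to yield an ultimate sample size of at least 180". The power statement there is for cytokine means only.

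**The concern.** The aim names symptoms, which are measured by a score. The analysis names cases and non-cases. A model for the risk of being a case, summarised by how well the whole model discriminates, does not estimate how depressive symptoms vary with ALLO. If the plan is followed as written, that part of Aim 2 is not reported, although suitable scores are scheduled.

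A binary outcome also usually carries less information than a score on the same construct, and this substudy is small for the purpose. Current major depression is excluded at entry and one third of the women are healthy controls, so PPD cases may be limited. With PPD undefined and the predictors described only as candidates, there is room to choose both after seeing the data.

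**Working it through.** **1. Does any other text cover a symptom score for Aim 2?** The Aim 2 paragraph opens by carrying over the Aim 1 approach, but it names anxiety as the dependent variable. The Aim 1 text does treat a measure both as dichotomous and as continuous, but that measure is HADS anxiety. The PHQ-9 appears as an outcome under the secondary efficacy endpoints of the main trial, where the comparison is between arms and ALLO plays no part. The mismatch rests on the text alone and needs no assumption.

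**2. Substudy size.** The plan's figure reproduces: 180 / (1 − 0.40) = 300 in total, and 60 / (1 − 0.40) = 100 per group.

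**3. What a binary outcome would keep.** The documents give no PPD rate for the substudy. The nearest figure is 30% in Section III item B, for depression and anxiety combined in the main trial. Prevalences of 10%, 20% and 30% are therefore assumptions. For a normal score cut so that a proportion p are cases, and a small effect, the efficiency of the binary analysis relative to the score is φ(z_p)² / [p(1 − p)], where φ(z_p) is the normal density at the cut. Effective n is 180 times this, and events are 180p.

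| Assumed p | Calculation | Information kept | Effective n of 180 | Events in 180 | Events per predictor, 5 candidates | Events per predictor, 2 candidates |
|---|---|---|---|---|---|---|
| 10% | 0.1755² / 0.09 | 0.34 | 62 | 18 | 3.6 | 9 |
| 20% | 0.2800² / 0.16 | 0.49 | 88 | 36 | 7.2 | 18 |
| 30% | 0.3477² / 0.21 | 0.58 | 104 | 54 | 10.8 | 27 |

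The candidate counts are illustrations. Five would be ALLO at the three pregnancy draws (baseline, 24 and 36 weeks) plus an intercept and slope for anxiety. Two would be one ALLO value and one anxiety summary. With ten, the range is 1.8 to 5.4.

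**4. Effect of attrition.** The 40% is an upper allowance; Section III item B reports up to 20% in the team's earlier clinic studies. At 20%, 300 × 0.80 = 240 women remain, giving 24, 48 and 72 events, or 4.8, 9.6 and 14.4 per predictor with five candidates.

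**5. Power, by simulation.** With 180 women, a normal score, an assumed correlation of 0.20 with the predictor and a 5% test, power is about 76% for the score. For logistic regression on the cut score it is about 35%, 45% and 53% at prevalences of 10%, 20% and 30%. At a correlation of 0.25 the figures are about 93% against 49%, 67% and 73%.

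**The case against.** A reader might infer that the plan dichotomises a score and so discards some 40% to 65% of the information. The documents do not support that. PPD is undefined, and a SCID diagnosis of MDE is scheduled at six weeks; the main trial also diagnoses MDE by SCID. If PPD means that diagnosis, the outcome is binary as measured and no score is cut. The efficiency formula compares a score with a cut of the same score; it does not compare an interview diagnosis with a different instrument. PHQ-9 may also be skewed in a sample that excludes current MDE and includes healthy controls. This objection stands, and it makes the figures conditional.

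A reader might also infer that there will be too few events per predictor, so that a null or chance ALLO finding is likely. That is not shown. At 180 women the ratio runs from about 2 to 27 depending on prevalence and a candidate count the plan does not give, and 180 is a minimum. Cross-validation already guards against overstated discrimination.

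The logistic model is legitimate in its own right. Section II cites the team's own finding that ALLO in pregnancy predicts the development of PPD, and a risk model with AUC addresses that directly. Demoting it or capping its predictors would be a preference.

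Finally, the protocol template asks only for a brief analysis plan, and the Missing Data section defers detail to an SAP to be finalised before unblinding. That explains missing definitions and predictor lists. It does not explain why the one depression analysis named for Aim 2 has a different outcome from the aim.

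**Conclusion.** The point holds as a mismatch between aim and analysis. The aim concerns symptoms, the only planned depression analysis is of an undefined binary PPD outcome, and the scheduled six-week scores are left out of it.

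The precision cost is an assumption-based range. The binary outcome keeps about 34% to 58% of the information at PPD prevalences of 10% to 30% if PPD is a cut of a roughly normal score and the effect is small. It is only indicative if PPD is the SCID diagnosis. Events in 180 women would be 18 to 54 over the same prevalences. Events per predictor cannot be fixed from the documents.

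The matter is confined to one half of one aim of the biological substudy. The primary endpoint of the trial is not affected.

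**What to change.** Add to the second part of Aim 2 a regression of the six-week PHQ-9 score on pregnancy ALLO, adjusted for study group (intervention, enhanced usual care, healthy control) and screening HADS depression, as the analysis that answers the symptom question. Use a linear model, or an ordinal model or transformed score if the distribution is skewed. State which pregnancy draw, or which summary of the draws, enters the model.

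Keep the logistic model and cross-validated AUC as the PPD risk-prediction analysis. State whether PPD means SCID MDE or a cut-off on a named score, and list the candidate predictors before the data are examined.

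Confirm that healthy controls complete the six-week PHQ-9. Table 4 marks it with the symbol for main-trial procedures, whereas substudy-specific procedures carry a different one, and healthy controls take part only in the biological study. If they do not complete it, either schedule it for them or restrict the analysis to the two randomised groups and say so.

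The cost is one extra analysis and some wording in the SAP. No new data are needed, provided healthy controls already complete the PHQ-9.
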